#### 4.1 Study schedule

Participants will be asked to attend the CRF on 6 occasions.

##### Visit 1- First Assessment Visit:

At the first visit, participants will be assessed for eligibility and those eligible will be requested to consent for further screening. Baseline outcome measurements will be conducted including weight/height/HR/blood pressure, ABPI, Treadmill assessments, questionnaires and taking of blood sample ([name] and/or Research Nurse). Participants will be fitted with the activPAL™ monitor and advised to wear this continuously for seven days. They will be given an instruction on how to use the activPAL, and provided with a sleep diary to complete during the duration of wearing the activPAL.

First Assessment Visit (90 mins)	Time (mins)	Responsible
Review of Inclusion/Exclusion Criteria Obtain Informed Consent	20	RN/UA
Participant demographics 

Gender / Date of birth / Height / Weight / Heart rate / Blood pressure

 Patient history 

Diagnosis of PAD (Date of diagnosis/Type of disease)

Present drug history (Statin/Antiplatelet/Anticoagulants)

Past Medical History (IHD/MI/LVH)

Cardiac risk factors (DM/Family History of IHD,CVA/Smoking: Current, Previous, Non-smoker/Alcohol excess: Current, Previous, Never/Hypercholesterolemia/Hypertension

	20	
Complete questionnaires: 

Generic quality of life questionnaire (SF-36)

Intermittent Claudication Questionnaire (ICQ)

Visual Analogue Scale (VAS)

Geriatric Depression Scale (Short Form) (GDS-SF)

Pain Self-Efficacy Questionnaire (PSEQ)

Illness Perception Questionnaire (IPQ)

	20	
Taking of blood sample	10	
Treadmill protocol 

ABPI assessment

McGill Pain Questionnaire (MPQ) (5 minutes post-treadmill protocol)

	20	
Fitting of ActivPAL to participants and instruction for use	20	

### Visit 2- Second Assessment Visit (usually within 2 weeks after visit 1):

Participants will then attend for a second visit to undergo a second Treadmill test, and to return the activPAL and sleep diary. Only participants with ≤20% variation in ACD will continue in the trial. After this visit eligible participants will be randomized, and given a date for them to return for intervention (TENS/Placebo ± Education) as applicable. Recruitment and randomisation will be done in waves to allow groups to be formed for the education session.

Second Assessment Visit (30 mins)	Time (mins)	Responsible
Return of ActivPAL by participants	5	RN/UA
Treadmill protocol • McGill Pain Questionnaire (5 minutes after completion of the treadmill protocol)	20	

### Visit 3- Intervention Visit (within 3 weeks after randomisation):

Participants attend the clinic to receive the TENS and training instructions for its daily use as required, plus or minus the patient education per randomization group. Participants allocated to receive education will undergo a group structured education session (4-6 persons per group). This intervention is adopted from the successfully piloted SEDRIC study: a one-off three-hour workshop of structured group education followed by three 2-weekly phone calls (see SEDRIC curriculum).

The aim of the structured education is to modify patients' illness beliefs and perceptions about IC/PAD by educating them on disease pathology and management philosophy. After the workshop, each patient will be supported to set goals for walking based around a pedometer and daily steps, develop an action plan regarding how these goals will be met and encouraged to repeat this process for each new walking goal through a 2-weekly phone calls from the educators (research team- [name] and Research Nurse) during which the progress, barrier and challenges are further discussed, and new walking goal will be set.

Before the education session, participants allocated to receive TENS will be provided with the device and instruction to use of the device. Also, the use of the device will be demonstrated, and patients shown how to put on and remove the device. Participants will try it out so on that to be sure they understand the procedure.

Intervention Visit (as per randomisation) (approx. 4 hours)	Time (mins)	Responsible
1. Education session + Placebo TENS & instructions for the use at home	240	CS + RN
2. Education session + Active TENS & instructions for the use at home	240	
3. Active TENS and instructions for use at home	60	
4. Placebo TENS and instructions for use at home	60	

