Methodology:	This a randomised controlled feasibility trial using a 2x2 factorial design of TENS versus placebo TENS with or without patient-centred education. Participants will be blinded to the type of TENS they receive. Outcome assessment of the primary outcome will be done by a blinded assessor.
Sample Size:	80
Screening:	Participants will be screened for eligibility by Research Nurse
Registration/Randomisation:	Randomisation by Robertson Centre for Biostatistics
Main Inclusion Criteria:	
 
• Clinical diagnosis of symptomatic Peripheral Arterial Disease (PAD) including resting ABPI <0.9 in at least one leg
 

	
 
• Stable IC for <math>\geq 3</math> months
 
• Walking limited primarily by claudication
 
• Able to exercise on a treadmill
 
• Able to read and speak English to a level allowing satisfactory completion of the study procedures
 
• Able to provide written informed consent for participation
 

Main Exclusion Criteria:	
 
• Planned surgical or endovascular intervention for PAD within the next 3 months
 
• Critical limb ischaemia
 
• The presence of any absolute contraindications to exercise testing/training as defined by the American College of Sports Medicine (ACSM)
 
• Previous experience of using TENS/ structured patient education for PAD
 
• Contraindications to TENS (including epilepsy, dermatological conditions, indwelling electrical pumps/pacemakers) and inability to apply TENS independently.
 
• Patients who require walking aids including artificial limbs
 
• Major surgery, myocardial infarction or stroke/ TIA in the previous 6 months
 
• Co-morbidities that cause pain or limit walking to a greater extent than IC (e.g. severe arthritis)
 
• <math>>20\%</math> variation in baseline ACD on treadmill
 
• Severe peripheral neuropathies above the ankle.
 
• Participation in another research protocol
 
• Participants <math>< 40</math> years of age
 

Product, Dose, Modes of Administration:	One-off 3 hours structured patient education + twice weekly phone call follow up to six weeks; High frequency TENS for daily use up to six weeks; placebo TENS for daily use for six weeks
Duration of Treatment:	Six weeks

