### 7.3 Recording and reporting of Adverse Events

We do not anticipate that the use of the CE-marked TENS device will result in any serious adverse events. Participants will be given prior information regarding the reporting of adverse events and measure to take including instructions to contact the research team via a dedicated phone line.

Participants will be specifically queried regarding the following adverse events of special interest: any case of itching, skin breakdown, mild electrical burn, other skin allergies, or mild autonomic responses at each study visit, and reported related adverse events will be documented in an applicable adverse event form.

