### **8.5 Safety analysis**

The safety data (adverse events)- both numbers of subjects and events – will be summarised by randomised group and overall using descriptive statistics. No formal statistical tests comparing the randomised groups will be pre-specified.

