Differences in the changes in activPAL outcomes, ICD, SF-36 and ICQ scores, MPQ score, IPQ, GDS-SF, PSEQ, ABI, and Biomarkers will also be analysed and effect scores calculated using Chi-squared tests, Mann-Whitney U or Wilcoxon signed-rank tests as applicable for between and within-group comparisons and log-rank method for pooled samples.

Safety analysis

The safety data (adverse events)- both numbers of subjects and events – will be summarised by randomised group and overall using descriptive statistics. No formal statistical tests comparing the randomised groups will be pre-specified.

Software for statistical analysis

The statistical software to be used is either SAS 9.2 for Windows, Cary, NC, USA or SPSS Version 22.

PrEPAID Statistical Analysis Plan (Version 1.0)
 Approval date:

Table 1: Participant characteristics at baseline

	PE+TENS	PE+ Placebo TENS	TENS	Placebo TENS
Age				
Sex (%male)				
Ankle-brachial index				
Diagnosis of PAD				
Date of diagnosis:				
\geq 3months <6months				
\geq 6months<12months				
\geq 12months				
Type of PAD				
Iliac				
Femoral				
Popliteal				
Other				
Diagnosis of IC				
Date of diagnosis:				
\geq 3months <6months				
\geq 6months<12months				
\geq 12months				
Limb affected				
Left				

PrEPAID Statistical Analysis Plan (Version 1.0)

Approval date:

Right				
Both				
Fontaine Classification				
I				
II				
III				
IV				
Past Medical History				
IHD: Y/N				
MI: Y/N				
LVH: Y/N				
Cardiac risk factors				
DM : Y/N				
Family History of IHD/CVA/ BP: Y/N				
Hypercholesterolemia: Y/N				
Hypertension: Y/N				
Alcohol excess:				
Current				
Previous				

PrEPAID Statistical Analysis Plan (Version 1.0)

Approval date:

Never				
Smoking:				
Current				
Previous				
Non-smoker				
Present drug history:				
Statin Y/N				
Antiplatelet Y/N				
Anticoagulant Y/N				
Outcome measures				
Treadmill maximal walking distance				
Treadmill pain free walking distance				
Daily steps				
Pain intensity(VAS)				
McGill pain score				
QoL SF-36 score				
ICQ score				
Geriatric depression questionnaire score				
Pain self-efficacy questionnaire score				
Brief illness perception questionnaire				

Table 2: Feasibility related outcome tables

Participants recruitment					
Total number of participants screened(n)					
Total number of eligible participants (n/%)					
Reasons for non-eligibility					
X (n/%)	Whole study sample	PE+TENS	PE+ Placebo TENS	TENS	Placebo TENS

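### Only the education arms have scheduled staff calls between device issue and Visit 4, so the by-arm adverse event summary may overstate reported events with education

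*Protocol*

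**What the plan says.** **Contact between Visit 3 and Visit 4.** Protocol Section 4 (Interventions) and the Visit 3 description give the education arms one group workshop and three calls at two-week intervals. The callers are the educators, who include the Research Nurse, and on the calls patients' walking plans are reviewed, "during which the progress, barrier and challenges are further discussed, and new walking goal will be set". The synopsis states another frequency: "One-off 3 hours structured patient education + twice weekly phone call follow up to six weeks". For the arms without education, the Visit 3 table has a 60-minute entry such as "3. Active TENS and instructions for use at home", and no call is listed before Visit 4.

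**Collection of adverse events.** Protocol 7.3 applies to all arms: "Participants will be specifically queried regarding the following adverse events of special interest", followed by a list of skin and mild autonomic events. The enquiry is made "at each study visit, and reported related adverse events will be documented in an applicable adverse event form". All participants are told of a phone line, and the Visit 4 table gives everyone a questionnaire on the listed events.

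**Analysis.** Under Protocol 8.5 the safety data "will be summarised by randomised group and overall using descriptive statistics". The SAP (Section 6, Safety analysis) says the same: "both numbers of subjects and events – will be summarised by randomised group and overall". No between-group test is planned. SAP Table 2 also has an adverse event rate entry under the four arm columns.

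Neither document says whether an event raised on an education call is recorded, or that the source of a report is kept.

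**The concern.** The number of occasions on which a participant can mention an event to study staff depends on the randomised arm. A patient with a skin reaction under the electrodes may well mention it when asked about barriers and challenges. Protocol 7.3 documents related events that are reported and does not restrict this to reports made at visits, so such a remark can reach the adverse event form. A patient without education who has the same reaction must phone in or recall it at six weeks.

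PE+TENS could then look less safe than TENS, and PE+placebo less safe than placebo, partly because of unequal ascertainment. Safety is part of the feasibility question (Protocol 2.3), and following adverse events in all groups is a stated objective (Protocol 2.2). With 20 participants per arm, one extra report moves an arm's rate by 1/20 = 5 percentage points. A descriptive table is usually read at face value.

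**Working it through.** **1. Numbers from the plan.** The documents give no adverse event rate or capture figure, so there is none to reproduce. Group sizes follow Protocol 8.7: 16 / (1 − 0.20) = 20 per arm and 4 × 20 = 80 in total, as stated. Each education level has 2 × 20 = 40 participants. Scheduled calls before Visit 4 are three per participant with education (3 × 40 = 120) and none without.

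**2. Model (illustrative).** All three of these inputs are assumptions:
- s: the chance that the Visit 4 questionnaire or phone line captures an affected participant, the same in all arms;
- c: the chance that one call captures a participant who would otherwise be missed;
- p: the true six-week risk, equal at both education levels.

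With k calls:
- capture without education = s
- capture with education = 1 − (1 − s)(1 − c)^k
- apparent risk ratio = [1 − (1 − s)(1 − c)^k] / s
- excess participants per 40 = 40 × p × [(1 − s) − (1 − s)(1 − c)^k]

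**3. Results with k = 3 and p = 0.20** (40 × 0.20 = 8 truly affected at each education level):

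| s | c | capture with education | ratio | excess per 40 |
|---|---|---|---|---|
| 1.0 | any | 1.000 | 1.00 | 0 |
| any | 0 | s | 1.00 | 0 |
| 0.9 | 0.1 | 0.927 | 1.03 | 0.2 |
| 0.9 | 0.3 | 0.966 | 1.07 | 0.5 |
| 0.7 | 0.1 | 0.781 | 1.12 | 0.7 |
| 0.7 | 0.3 | 0.897 | 1.28 | 1.6 |
| 0.5 | 0.1 | 0.635 | 1.27 | 1.1 |
| 0.5 | 0.3 | 0.829 | 1.66 | 2.6 |

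Example, last row: 1 − 0.5 × 0.7³ = 1 − 0.5 × 0.343 = 0.829; 0.829 / 0.5 = 1.66; 8 × (0.829 − 0.5) = 2.6.

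**4. Sensitivity to the number of calls.**
- If the synopsis is read literally, 2 × 6 = 12 calls. The ratio is then 1.08 to 1.11 at s = 0.9 and 1.72 to 1.99 at s = 0.5, for c from 0.1 to 0.3.
- If three calls fall at weeks 2, 4 and 6, the last coincides with Visit 4 and adds little. With k = 2, s = 0.5 and c = 0.3, capture is 1 − 0.5 × 0.49 = 0.755, the ratio is 0.755 / 0.5 = 1.51 and the excess is 8 × 0.255 = 2.0.

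**5. Limits.** The model lets every call find every missed participant, although an early call cannot reveal a later event, so the upper end is generous. It counts participants, not events.

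**6. Which contrasts are affected.** PE+TENS and PE+placebo have the same call schedule, and TENS and placebo TENS both have none. The asymmetry falls on education versus no education, not on active versus placebo within an education level.

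**The case against.** The strongest reply is that ascertainment is common where it matters. Every arm has the same Visit 4 questionnaire, the enquiry at visits and the phone line. The calls exist for walking goals, list no adverse event enquiry and are not study visits. If the common routes capture the listed events, there is no bias. The analysis is descriptive, no error rate is affected, and the only numerical feasibility triggers in Protocol 8.2 (10% eligible, 10% agreeing) do not use adverse events.

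Much of this stands: it makes a ratio of 1.00 a real possibility and limits the consequence. It does not close the gap. The Visit 4 questionnaire covers only the listed events, the phone line depends on the participant, and no visit falls between Visits 3 and 4. The plan also allows 20% attrition, so up to 0.20 × 40 = 8 participants without education might leave with no solicited enquiry after device issue, whereas those with education might already have been called.

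A reader might infer more than the documents support:
- **That education will certainly look more harmful.** Nothing says that remarks on calls enter the record, and advice on a call could prevent a repeat event.
- **That the events are too short-lived to be recalled at six weeks.** No duration is given, and the list includes skin breakdown and mild burn.
- **That education patients wear the unit throughout the 240-minute visit.** Visit 3 says only that they try it before the session.
- **That any excess is an artefact.** Education promotes walking, and Protocol 6.1.1 and 6.2.1 tie device use to standing and walking, so true exposure may rise.
- **That the ratio is at least 1.15.** With even onset, 4/6 = 0.667 of events start more than two weeks before Visit 4. Losing 20% to 50% of these gives 0.667 × 0.20 = 0.13 to 0.667 × 0.50 = 0.33 missed, and ratios of 1/0.87 = 1.15 to 1/0.67 = 1.5. That assumes full capture with education and excludes no bias by construction.

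**Conclusion.** The point holds as a possible bias. Scheduled contact between device issue and Visit 4 differs by education allocation, the handling of events raised on calls is unspecified, and the by-arm summary pools all sources. Reported events may be overstated with education relative to no education. Active versus placebo TENS within an education level, which is the device-safety question, is largely protected.

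The size is unknown. With three calls, s from 0.5 to 1 and c from 0 to 0.3, the apparent ratio runs from 1.00 to about 1.7. At an assumed 20% risk that is 0 to about 2.6 extra participants per 40. These capture rates and the risk are assumptions, and the number of calls is itself unsettled between the synopsis and the body of the protocol. The plan as written could not separate extra reporting from a real effect of greater device use.

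The change is worth making because it is cheap and a report's source may not be recoverable later.

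**What to change.** 1. **Adverse event form:** add a source field with the values Visit 3 on site, education call, phone-in, Visit 4 questionnaire and other visit. Complete it when the event is recorded.
2. **Protocol 8.5 and SAP Section 6:** keep the all-source table by arm, with call-only events as a separate row. Add a by-arm table of events elicited by the Visit 4 questionnaire, with the number completing it as denominator and one look-back period covering the whole six-week intervention.
3. **Interpretation, stated in the SAP:** read education versus no education from the solicited table, and device harm from active versus placebo TENS within each education level.
4. **Consistency:** reconcile the call frequency in the synopsis with Section 4 and Visit 3, since it sets the size of the asymmetry. Also reconcile the enquiry at each visit in 7.3 with the Visit 5 table, which lists no adverse event questionnaire.

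The cost is one form field, about two SAP sentences and one extra table, with no extra calls or staff. The solicited table omits participants who leave before Visit 4, and it excludes events known only from phone-in, so it should stand beside the all-source table and not replace it. Better recall among participants who were called may remain. SAE reporting is unchanged.

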### Interventions:

**TENS:** Participants will be given TENS at intervention visit. They will be instructed to use the device daily at home or elsewhere. They will be specifically advised to use the device prior to, or during, a challenging walk each day. Challenging walk could be for activities of daily living (ADL) or planned exercise. For those with bilateral claudication they are advised to wear the device on the worst limb and could alternate it as symptoms fluctuates. The active group will receive High Frequency-TENS (120 Hz, 200µs and a patient-determined intensity of “strong but comfortable”).

**Placebo TENS:** Participants will receive the same model and instructions for use as those in the active group except that the stimulation dose is be safely altered to produce non-therapeutic, ineffective stimulation. For the purposes of blinding, participants will be told that different dosages of TENS are being tested some of which they might not feel anything even though the device is working. This method of effecting placebo has been successfully used in previous TENS trials.

Both the statistician conducting the randomization and the outcome assessor would be blinded to active TENS and placebo TENS. Importantly, participants will receive the same set of instructions as those in active TENS with the addition of a statement that two TENS are being tested. Blinding will be assessed at the end of the intervention period. Participants will be asked if they believed their TENS unit was functioning properly.

**Patient-Centred Education:** Intervention in these groups will be adopted from the successfully piloted SEDRIC study: A one-off three-hour workshop of structured group education (4-5 persons in each group) and three 2-weekly phone calls. Two educators will implement the session. Training for educators will involve completion of the DESMOND core training, reading and demonstrating understanding of the SEDRIC curriculum, and completion of at least two practice workshops that are

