## 6.2 Placebo TENS:

Placebo effect has been reported while using TENS in other conditions therefore, testing active TENS against placebo is advocated. The same model as used in active TENS will be used in the placebo TENS group but an infective setting (current intensity of about 6mA) will be used. Patients will be told that different doses of TENS are being tested. This will allow the unit to be switched on with the appearance of a working unit. All TENS units will be calibrated, checked and confirmed prior to being issued to participants. This method of achieving placebo has been successfully used in previous TENS trials.

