Trial design:

We will conduct a 2 x 2 parallel group (TENS versus placebo TENS x SEDRIC versus no additional education) feasibility RCT to compare use of TENS against placebo TENS with and without a patient-centred education programme. Permuted block randomisation will be implemented to allocate patients to trial arms. The intervention will last for 6 weeks, and patients recruited within the first eight months will be further followed up for 3 months. Outcomes assessments will be implemented at baseline, after six weeks treatment and at 3 months follow up. We will collect information regarding the recruitment rate, intervention uptake, outcome measure completion rate, attrition rate, blinding fidelity, efficacy related to the primary, secondary and other PROMs, and patients experience of intervention including acceptability and ease of intervention.

Randomisation:

A central randomisation facility (interactive voice response system, IVRS) will allocate the randomised therapy per patient. The IVRS, based at the Data Centre, will be available by telephone. Stratified permuted block randomization procedures will be utilised to allocate patients to groups (Patients allocation will be stratified by gender and age, ABPI values). Permuted block design (PBD) will be used to allocated patients to the PE+TENS, PE+Placebo TENS, TENS, Placebo TENS using 4-way randomisation throughout the whole time until the recruitment of a minimum of 20 subjects in the each of the larger comparison groups are achieved.

Sample size:

Details regarding sample size calculation can be found in section 8.7 of the full study protocol (version 2.0). Summarily, 16 participants per group will allow detection of an effect size of 1.0sd of ACD in active TENS group compared to placebo control. Allowing for 20% attrition, we will recruit 20 participants in each group, and therefore aim to recruit 80 patients.

Framework

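### Education-arm participants try their TENS unit before a three-hour group workshop, and nothing in the plan stops active and placebo users from comparing sensations

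*Protocol*

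**What the plan says.** Protocol section 4.1, Visit 3, sets the order of events: "Before the education session, participants allocated to receive TENS will be provided with the device and instruction to use of the device". It adds: "Participants will try it out so on that to be sure they understand the procedure". The phrase about being allocated to receive TENS might look like active units only. However, the Visit 3 table lists education with placebo TENS alongside education with active TENS, and the Placebo TENS text gives placebo users the same model and instructions.

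The workshop that follows is described in the Interventions section: "A one-off three-hour workshop of structured group education (4-5 persons in each group) and three 2-weekly phone calls". Visit 3 gives the group size as 4-6. On how groups arise, Visit 2 says: "Recruitment and randomisation will be done in waves to allow groups to be formed for the education session". The SAP (Randomisation) says: "Permuted block design (PBD) will be used to allocated patients to the PE+TENS, PE+Placebo TENS, TENS, Placebo TENS using 4-way randomisation".

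Active TENS is adjusted by the patient to a strong but comfortable level (Interventions; section 6.1). Placebo TENS is fixed at about 6 mA, intended to have no effect (section 6.2). The protection at participant level is the explanation given to them: "participants will be told that different dosages of TENS are being tested some of which they might not feel anything". They are also told that two kinds of TENS are under test. Blinding is checked only afterwards, at the end of the intervention (protocol) or on leaving the study (SAP).

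**The concern.** The two settings are meant to feel different. The explanation given to participants accounts for a unit that cannot be felt, but it does not hide the contrast from people who can compare notes. In the education arms, participants have just felt their own unit when they begin three hours together. Participants in the other two arms have no scheduled group contact until the focus groups, which follow the final follow-up.

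The outcomes are open to expectation. Absolute claudication distance (ACD) ends when the patient can no longer tolerate walking (Glossary), and the questionnaire outcomes are self-reported. A blinded treadmill assessor does not protect against what the participant believes. Section 1.2 says that TENS has a strong placebo effect, which is the trial's reason for having a placebo.

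Any loss of blinding would sit in one half of the 2 x 2 design. It could bias education plus TENS against education plus placebo, a comparison named in the SAP under Framework, and it could distort the TENS effect with education relative to that without. Blinding fidelity is also a feasibility outcome, so a poor result could reflect the order of one visit and not the placebo method that a definitive trial would inherit.

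**Working it through.** **Numbers exposed.** Protocol section 8.7 plans 16 evaluable per group and 20% attrition: 16 / (1 - 0.20) = 20 per group, and 4 x 20 = 80, as stated. Two arms receive education: 2 x 20 = 40, of whom 20 are active and 20 placebo, taking the four-way allocation as equal.

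**Chance that a session is mixed.** The documents give no figure. Assume that a session of k people is filled without regard to TENS type.

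- Binomial, each person active with probability 0.5: P(mixed) = 1 - 2 x 0.5^k.
- Hypergeometric, k drawn from 20 active and 20 placebo: P(mixed) = 1 - 2 x C(20,k) / C(40,k).

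| k | Binomial | Hypergeometric | Sessions for 40 people | Expected single-type sessions (binomial) |
|---|---|---|---|---|
| 4 | 1 - 0.125 = 87.5% | 89.4% | 10 | 10 x 0.125 = 1.25 |
| 5 | 1 - 0.0625 = 93.8% | 95.3% | 8 | 8 x 0.0625 = 0.5 |
| 6 | 1 - 0.03125 = 96.9% | 98.0% | 6.7 | 6.7 x 0.03125 = 0.2 |

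**Effect of blocking.** The SAP uses permuted blocks but does not state the block size. A simulation that assumed unstratified blocks of 4 or 8 and grouped consecutive education participants gave 100% mixed sessions for k = 4, 5 and 6. The SAP also stratifies by gender, age and ABPI, which loosens the balance within a wave. The binomial range is therefore the cautious one.

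**Opposite assumption.** If sessions were held separately by TENS type, the figure would be 0%. Neither document says that they are.

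**Time for fitting.** An education visit is 240 minutes and the workshop is 180, leaving 240 - 180 = 60 minutes. Two staff roles are listed, so 2 x 60 = 120 staff-minutes: 120 / 6 = 20 minutes each for six people, or 120 / 4 = 30 minutes each for four.

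**The case against.** The strongest reply is that several links in the chain are not in the documents. They do not say that sessions mix TENS types, that units are fitted in view of others, or that units run during the workshop. Participants are told to switch on when standing, walking or about to do something likely to bring on pain, which does not describe a seated session. Hearing that a neighbour feels more is also consistent with having been told that different dosages are under test. All of this stands, and it makes the point one of risk.

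Three stronger readings are tempting and should be resisted.

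- A reader might take the 60 minutes left in the education visit as evidence that units are fitted in parallel in a group. The same 60 minutes allows 20-30 minutes of individual fitting with two staff, so the timetable settles nothing.
- A reader might take 87.5-96.9% as a rate of unblinding. It is the chance of a mixed session, and nothing in the documents links that to loss of blinding or to a shift in ACD.
- A reader might think that differential unblinding would go unseen. SAP Table 2 already has a TENS blinding row with a column for each of the four arms, so no change to reporting is needed. That row would show a difference but could not undo it.

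What the reply does not answer is the order itself. Followed as written, the protocol has people feel their unit and then sit together for three hours, with no stated safeguard. Knowing that two kinds of TENS are under test gives them a reason to work out which they have.

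**Conclusion.** The point holds as a risk to participant blinding that falls only in the two education arms, at most 40 of 80 participants. If sessions are filled without regard to TENS type and allocation within education is 1:1, between 7 in 8 sessions (groups of four) and 31 in 32 (groups of six) would contain both kinds of user. The documents do not support saying that blinding will fail, nor putting a size or direction on any bias. The sample size is unaffected. The visit order should be changed, because it works against the blind and can be altered cheaply. If separate sessions or private fitting are already intended, the protocol needs to say so.

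**What to change.** In protocol section 4.1, Visit 3:

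- Move device issue, demonstration and try-out from before the workshop to after it.
- State that each participant is fitted individually, out of sight and hearing of the others, and does not rejoin the group afterwards.
- Add a request that participants do not discuss what they feel from the unit with one another.
- Reconcile the group size (4-5 in the Interventions section, 4-6 under Visit 3).

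With two staff working separately, this fits the existing 60 minutes at 20-30 minutes each, with no extra visit. It has a cost. In a group of six, fitted in three rounds of 20 minutes, the last pair waits 40 minutes. Education-arm participants would also have less fitting time than the 60 minutes allotted in the other arms. If post-workshop goal-setting falls outside the three hours, it competes for the same time. Contact between participants after the visit cannot be ruled out, only discouraged.

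Forming sessions by TENS type would bring mixing to 0%, but at 4-6 people per education arm each wave would need about 16-24 randomised participants, against about 8-12 for a mixed session. That is hard to reconcile with an intervention visit due within three weeks of randomisation, so re-ordering is the lighter change.
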